8.2 Sample Size Determination

The One-Sample Proportion Test is used to calculate the sample size. The required sample size was calculated assuming the true proportion is 0.95, the test is one-sided exact binomial, $\alpha = 0.025$, and the power is $1 - \beta = 0.90$. The P30 sample size calculation yields 102 subjects. However, to remain consistent with the previous sample size from the pivotal study (protocol 100-003) for the TGFR, the study will enroll 140 evaluable subjects.

Statistical Analysis Plan		Page 26 of 29
MediBeacon Inc.	An Open Label, Multi-Center, Safety and Pharmacokinetic Bridging Study of MB-102 (Relmapirazin) and the Use of the MediBeacon [®] Transdermal GFR Measurement System using the TGFR Reusable Sensor with Disposable Adhesive Ring in Normal and Renal Compromised Subjects for the Evaluation of Kidney Function	Ver 4.0

An adaptive trial design will be employed for the reusable sensor as follows:

- 1. Run-in cohort of up to 30 evaluable subjects will commence the study. Additional Run-in subjects may be enrolled at new clinical sites to ensure protocol compliance. Run-in subject data will be considered tuning data.
- 2. Validation Cohort 1 (approximately 20 evaluable subjects) will be used to confirm final algorithm selection. Validation Cohort 1 subject data will be considered tuning data.
- 3. Validation Cohort 2 (approximately 75 evaluable subjects) will be analyzed in an interim analysis to compare results against the primary endpoint specification. At that time, the primary endpoint null hypothesis will be tested using an exact binomial test at a one-sided nominal alpha level of 0.0150 using the method of Pocock for a two-stage design with the interim analysis performed based on the first 53.57% of the planned number of subjects. At the final analysis, the primary endpoint null hypothesis will also be tested at a one-sided nominal alpha level of 0.0150. This will control the overall Type I error rate at the one-sided 0.025 level.
- 4. If the primary endpoint has been achieved, the study will be terminated. If not, the trial will be continued.
- 5. Validation Cohort 3 (approximately 65 evaluable subjects) will be enrolled in the event the interim analysis did not meet the primary outcome measure. Final analysis will be of the 140 evaluable subjects.

The subjects will be chosen to span the range of renal function from normal to Stage 4 CKD impaired. The protocol will target enrolling 50% of subjects in the Fitzpatrick Skin Scale range of I-III and 50% within Fitzpatrick Skin Scale range of IV-VI.

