9.7 Determination of Sample Size

For a P30 true value of 0.95, alpha of 0.025, performance goal of 85%, power of 90%, the one-sided exact binomial test yields a sample size of 102.

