3.1 Primary Objective and Endpoint

The primary objective is to establish that MB-102 transdermal fluorescence measured GFR using the MediBeacon[®] Transdermal GFR Measurement System is comparable to the measured MB-102 indexed plasma GFR.

The primary endpoint is the performance measure of P30 for transdermal-derived GFR with respect to the plasma-derived indexed GFR, with a 95% confidence interval. The performance goal is 85%. Success for the study will be that the lower limit of the 95% CI is greater than 85%.

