3.3 Safety Evaluation

Safety of MB-102 will be evaluated through treatment emergent adverse events (TEAEs), where treatment emergence is defined with respect to the first administration of MB-102.

Safety of the MediBeacon® Transdermal GFR Measurement System will be evaluated through TEAEs, where treatment emergence is defined with respect to the start time of device use. Additional safety variables include physical examinations, clinical laboratory assessments, ECGs, and concomitant medication use. All clinically significant findings in physical examinations, clinical laboratory assessments and ECGs will be reported as an AE or as medical history (if observations are noted prior to dose administration).

Statistical Analysis Plan		Page 12 of 29
MediBeacon Inc.	An Open Label, Multi-Center, Safety and Pharmacokinetic Bridging Study of MB-102 (Relmapirazin) and the Use of the MediBeacon [®] Transdermal GFR Measurement System using the TGFR Reusable Sensor with Disposable Adhesive Ring in Normal and Renal Compromised Subjects for the Evaluation of Kidney Function	Ver 4.0

4 Analysis of Primary Endpoint

The primary endpoint is the performance measure of P30 for transdermal-derived GFR with respect to the plasma-derived indexed GFR, with a 95% confidence interval. The performance goal is 85%. Success for the study will be that the lower limit of the 95% CI is greater than 85%.

The primary endpoint will be calculated for subjects enrolled into the Validation 2 and 3 (if applicable) cohorts only. The Run-in cohort and Validation 1 cohort enrollment were performed to provide final tuning data and used for software updates.

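### The SAP holds two success rules, an exact test at 0.0150 and an unadjusted 95% CI, which disagree at 70/75 and 128/140; it gives no counts or power for the two-look design

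*SAP*

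**What the plan says.** **The test.** SAP 8.2 and Protocol 9.5 test the primary null hypothesis with an exact binomial test at one-sided nominal 0.0150, after about 75 evaluable subjects (Validation Cohort 2) and again at 140. The level comes from Pocock's method at an information fraction of 53.57%, and overall one-sided error is said to be held at 0.025. On the second look: "At the final analysis, the primary endpoint null hypothesis will also be tested at a one-sided nominal alpha level of 0.0150".

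**The success criterion.** SAP 3.1 reads: "Success for the study will be that the lower limit of the 95% CI is greater than 85" (per cent). SAP 4, the Protocol synopsis and the opening of Protocol 9.5 repeat it. None of them mentions the interim look or another confidence level. SAP 8.9 stops the trial at the interim if the primary endpoint has been reached, without saying which rule decides that.

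**The sample size.** Protocol 9.7 gives "alpha of 0.025, performance goal of 85%, power of 90%, the one-sided exact binomial test yields a sample size of 102", for a true P30 of 0.95. SAP 8.2 repeats the 102 and then says that, for consistency with the earlier pivotal study, "the study will enroll 140 evaluable subjects". Neither document gives critical counts, attained error or power for the 75/140 design.

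**The concern.** A one-sided test at 0.0150 corresponds to a 98.5% one-sided exact limit (two-sided 97%). A two-sided 95% interval corresponds to 0.025. The two rules therefore cannot always agree, and the SAP does not say which governs. The clause in SAP 1 that lets the SAP prevail over the protocol does not help, because both rules are in the SAP.

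At stake are whether the trial stops at the interim, whether a borderline final count is a success, and whether the overall error is the claimed 0.025. Separately, binomial counts are discrete, so an exact test held to 0.0150 can leave part of the 0.025 unused. The only power statement is for a test the trial will not run, so the reader cannot see what that costs.

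**Working it through.** **Inputs.** Null P30 0.85 (performance goal, SAP 3.1 and 4); true P30 0.95, one-sided alpha 0.025 and power 0.90 (SAP 8.2, Protocol 9.7); looks at 75 and 140 with nominal 0.0150 at each (SAP 8.2). True P30 values below 0.95 are my assumption, shown as a range. The success criterion names no interval method; I take Clopper-Pearson, the exact method that SAP 8.6 names for categorical variables.

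**1. The plan's own figures.** With T(n, r, p) = P(X ≥ r) for X ~ Bin(n, p), the smallest r at n = 102 with T(102, r, 0.85) ≤ 0.025 is 94: error 0.0231, power T(102, 94, 0.95) = 0.930. Exact power first touches 90% at n = 93, and 102 is the smallest n from which it stays at or above 90% for every n checked, up to 199. So 102 is reproduced for a single look. The Pocock level at fraction 75/140 = 0.5357 comes out at 0.0149, against 0.0150 stated.

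**2. Counts implied by the 0.0150 test.**
- Interim: T(75, 70, 0.85) = 0.0234 fails; T(75, 71, 0.85) = 0.0084 passes. Cut 71/75.
- Final: T(140, 128, 0.85) = 0.0170 fails; T(140, 129, 0.85) = 0.0083 passes. Cut 129/140.

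**3. Counts implied by the 95% CI rule.** The lower limit for x of n is the 0.025 quantile of Beta(x, n − x + 1). It is 85.1% at 70/75 and 85.5% at 128/140, so both counts succeed by the CI and fail the 0.0150 test. At 127/140 it is 84.6%, so 128 is the CI cut.

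**4. Overall probability of success.** For cuts r1 and r2,

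P(success) = T(75, r1, p) + Σ over x < r1 of P(X = x of 75) × T(65, r2 − x, p).

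At p = 0.85:

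| Cuts | Interim | Final look | Overall error |
|---|---|---|---|
| 71/75, 129/140 (0.0150 test) | 0.0084 | 0.0061 | 0.0145 |
| 71/75, 128/140 | 0.0084 | 0.0137 | 0.0221 |
| 70/75, 128/140 (95% CI at both looks) | 0.0234 | 0.0104 | 0.0338 |

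**5. Power.**

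| True P30 | Cuts 71, 129 | Cuts 71, 128 | Gain (points) |
|---|---|---|---|
| 0.95 (the plan's value) | 95.6% | 97.8% | 2.2 |
| 0.94 | 87.5% | 92.5% | 5.1 |
| 0.93 | 74.4% | 82.6% | 8.2 |
| 0.92 | 58.2% | 68.4% | 10.2 |
| 0.91 | 41.8% | 52.1% | 10.3 |
| 0.90 | 27.7% | 36.6% | 8.9 |

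Gains are taken from unrounded powers. The largest is 10.5 points, near 0.914. The chance of stopping at the interim at 0.95 is T(75, 71, 0.95) = 67.9%.

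**6. How often the rules collide.** At true P30 0.95, exactly 70/75 has probability 14.9%. Reaching the final look and ending at exactly 128/140 has probability 2.2%, which is the power gain in step 5.

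**7. Sensitivity to the evaluable numbers.** The cohorts are only approximately sized. At 75/142 the 0.0150 test gives cuts 71 and 130 with error 0.0199; a final cut one lower gives 0.0321. At 75/137, a final cut one lower gives 0.0262. Neither size allows the one-count gain.

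**The case against.** The strongest defence is that the testing rule is sound. Its exact error is below 0.025, as claimed. Equal nominal levels at each look are a legitimate choice, and declining to use leftover alpha is no mistake. At the only true P30 the plan assumes, power is 95.6%, above both the 90% target and the 93.0% of the single-look test with 102. SAP 8.2 itself moves from 102 to 140 in the same paragraph. The unused error is also particular to 75/140; two more subjects at the final look remove most of it. All of this stands.

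Three stronger readings are tempting and are not supported:
- **That the 0.0150 rule fails to control error.** It does control it. Only the CI rule used at both looks exceeds 0.025.
- **That the design gives away 10 points of power.** That needs a true P30 of about 0.91 to 0.92, which the documents never assume. At 0.95 the cost is 2.2 points.
- **That the 102-subject statement is wrong or causes a power loss.** It is correct for a single look. The loss comes only from the discrete final cut of 129 rather than 128.

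The sponsor may add that the CI sentence merely describes the endpoint while the 0.0150 test decides. The documents do not say so. The sentence is worded as the criterion for study success, so it cannot be set aside; nor can it be said that 128/140 would definitely be declared a failure.

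Lowering a cut in an open-label, single-arm trial also raises a question of timing. SAP version 4.0 is dated 18 September 2024, after the planned study end of Q2 2024, and its section 4 describes the tuning cohorts in the past tense. The documents do not show whether interim results had been seen.

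**Conclusion.** The concern holds as an inconsistency in the success rule plus a reporting gap. The two rules give different answers at 70/75 and 128/140, and the unadjusted CI rule at both looks has overall error 0.0338 against a claimed 0.025. The 0.0150 rule alone is valid and conservative at 0.0145. The boundary 71/75 or 128/140 stays within 0.025 (0.0221) and adds 2.2 points of power at P30 0.95, rising to about 10 only near 0.91 to 0.92. The actual design exceeds 90% power at 0.95, but the plan does not report this.

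These figures rest on exactly 75 and 140 evaluable subjects, independent binomial outcomes and a Clopper-Pearson interval. Other evaluable numbers change both the counts and the attained error.

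**What to change.** 1. State one success rule everywhere, as exact counts with overall exact one-sided error at most 0.025. At 75/140: at least 71/75 at the interim or at least 128/140 at the final, error 0.0221. Say that the cuts are recomputed exactly for the actual evaluable numbers, since the one-count gain is not available at every size.
2. Replace the unadjusted 95% CI criterion with this rule in SAP 3.1 and 4, the Protocol synopsis and Protocol 9.5. Refer to it in SAP 8.2 and 8.9.
3. Beside the 102-subject statement in SAP 8.2 and Protocol 9.7, give the power of the two-look design: at P30 0.95, 67.9% chance of success at the interim and 97.8% overall.
4. Fix the cuts before the outcome data are seen. If that is no longer possible, keep the 0.0150 test (71/75, 129/140), state its error of 0.0145 and power of 95.6% at 0.95, and use a one-sided 98.5% (two-sided 97%) exact lower limit above 85% as the criterion. That limit is 84.2% at 70/75 and 84.8% at 128/140 (both fail), and 86.0% at 71/75 and 85.7% at 129/140 (both pass), so it agrees with the test.

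**Cost.** Wording in both documents and no extra subjects. Under option 1 the nominal level is no longer equal at the two looks, which needs a line of explanation.

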5.1 Overall Study Design and Plan

Protocol 100-201 is a multi-center, open-label, adaptive bridging investigation studying the safety and pharmacokinetics of MB-102 and the use of the MediBeacon[®] Transdermal GFR Measurement System with the TGFR reusable sensor with disposable adhesive ring in normal and compromised renal function subjects with different skin color types comparing tGFR to plasma derived indexed GFR (nGFR).

Up to 240 subjects are planned to be dosed. The population will be split into stratums in accordance with eGFR by the CKD-EPI equation (pre- 2021) (Levey et al., 2009). The study will enroll into 4 consecutive cohorts:

1. A **Run-in Cohort** of up to 30 evaluable subjects will be enrolled to test monitor algorithm settings with the TGFR reusable sensor with disposable adhesive ring. Additional Run-in subjects may be enrolled at new clinical sites to ensure protocol compliance. Run-in subject data will be considered tuning data.

The following will be enrolled into the Run-in cohort:

- At least 5 subjects will be enrolled in Stratum 2
- At least 4 subjects in each of the FSS I-II; III-IV and V-VI

Clinical sites not yet active on the trial may also be required to participate in the Run-in Cohort in order to demonstrate protocol compliance prior to participating in the Validation 2 Cohort or Validation 3 Cohort.

- 2. Validation Cohort 1 (approximately 20 evaluable subjects) will be used to confirm final algorithm selection. Validation Cohort 1 subject data will be considered tuning data.
- 3. Validation Cohort 2 (approximately 75 evaluable subjects) will be analysed in an interim analysis to compare results against the primary endpoint specification. If the primary endpoint has been achieved, the study will be terminated. If not, the trial will be continued.

4. Validation Cohort 3 (approximately 65 evaluable subjects) will be enrolled in the event the interim analysis did not meet the primary outcome measure. Final analysis will be of the 140 evaluable subjects.

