9.5 Primary Endpoint Analysis

The primary endpoint is the performance measure of P30 for transdermal-derived GFR with respect to the plasma-derived indexed GFR, with a 95% confidence interval. The performance goal is 85%. Success for the study will be that the lower limit of the 95% CI is greater than 85%.

Prior data demonstrated for a P30 true value of 0.95, alpha of 0.025, performance goal of 85%, power of 90%, the one-sided exact binomial test yields a sample size of 102. As the reusable sensor is new, an adaptive trial design will be employed.

A Run-in Cohort of up to 30 evaluable subjects will be enrolled to test monitor algorithm settings with the TGFR reusable sensor with disposable adhesive ring. Additional run-in subjects may be enrolled at new clinical sites to ensure protocol compliance. Run-in subject data will be considered tuning data. The following will be enrolled into the run-in cohort:

- At least 5 subjects will be enrolled in Stratum 2
- At least 4 subjects in each of the FSS I-II; III-IV and V-VI
- Validation Cohort 1 (approximately 20 evaluable subjects) will be used to confirm final algorithm selection. Validation Cohort 1 subject data will be considered tuning data.
- Validation Cohort 2 (approximately 75 evaluable subjects) will be analysed in an interim analysis to compare results against the primary endpoint specification. At that time, the primary endpoint null hypothesis will be tested using an exact binomial test at a one-sided nominal alpha level of 0.0150 using the method of Pocock for a two-stage design with the interim analysis performed based on the first 53.57% of the planned number of subjects. At the final analysis, the primary endpoint null hypothesis will also be tested at a one-sided nominal alpha level of 0.0150. This will control the overall Type I error rate at the one-sided 0.025 level.

- If the primary endpoint has been achieved, the study will be terminated. If not, the trial will be continued.
- Validation Cohort 3 (approximately 65 evaluable subjects) will be enrolled in the event the interim analysis did not meet the primary outcome measure. Final analysis will be of the 140 evaluable subjects.

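### The interim rule allows only success or continuation, so about 65 more evaluable subjects are enrolled even when primary success has become arithmetically impossible

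*SAP*

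**What the plan says.** SAP 8.2 states that "Validation Cohort 2 (approximately 75 evaluable subjects) will be analyzed in an interim analysis", with the primary null hypothesis "tested using an exact binomial test at a one-sided nominal alpha level of 0.0150". What follows is "If the primary endpoint has been achieved, the study will be terminated. If not, the trial will be continued". Protocol 5.1 says of Validation Cohort 3 (about 65 evaluable subjects) that it "will be enrolled in the event the interim analysis did not meet the primary outcome measure". Protocol 5.4.1 and 9.5 and SAP 8.9 give the same two-way rule. On the last look, Protocol 9.5 says: "At the final analysis, the primary endpoint null hypothesis will also be tested at a one-sided nominal alpha level of 0.0150".

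SAP 3.1 and SAP 4 word success differently: "Success for the study will be that the lower limit of the 95% CI is greater than 85" percent, with no adjustment for the interim look.

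The sponsor's termination right in Protocol 5.4.4 covers a safety issue or special circumstances that make further treatment impossible. The Safety Review Committee (Protocol 7.2, SAP 7.1) oversees safety data. Neither provision deals with an effectiveness endpoint that can no longer be met.

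**The concern.** The final analysis pools Cohorts 2 and 3, so misses in Cohort 2 are carried forward. Beyond a certain number of them, no result in Cohort 3 can bring the pooled count up to the success criterion. The rule does not recognise that state and sends the trial on to 140.

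At stake is the exposure of about 65 further evaluable subjects, plus any replacements. Each receives an intravenous investigational tracer, 14 (Stratum 1) or 17 (Stratum 2) PK draws counting the pre-dose sample, and 12 or 24 hours of collection. By design, half of them have an eGFR below 70. Protocol 9.5 gives the newness of the reusable sensor as the reason for an adaptive design, so the interim ought to deal with poor performance as well as good.

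**Working it through.** **Inputs.** Performance goal p0 = 0.85 (SAP 3.1); planning value 0.95 (Protocol 9.7: "For a P30 true value of 0.95"); interim n = 75 and final n = 140 (SAP 8.2); exact binomial test at one-sided 0.0150 at both looks (SAP 8.2, Protocol 9.5). A hit is a tGFR that meets P30; a miss is one that does not. Cohort sizes are given as approximate, and exactly 75 and 65 are assumed here.

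**The plan's own figure.** Protocol 9.7 states: "alpha of 0.025, performance goal of 85%, power of 90%, the one-sided exact binomial test yields a sample size of 102". With r the smallest count for which P(X ≥ r | n, 0.85) ≤ 0.025, n = 102 gives r = 94, exact alpha 0.0231 and power 0.930 at 0.95. Power stays at or above 0.90 for every larger n checked (to 159), and it is below 0.90 for n = 95 to 101. The 102 is reproduced.

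**Cut-offs at 0.0150.**
- Interim, n = 75: P(X ≥ 71) = 0.0084 and P(X ≥ 70) = 0.0234. Success needs 71 hits, so at most 4 misses.
- Final, n = 140: P(X ≥ 129) = 0.0083 and P(X ≥ 128) = 0.0170. Success needs 129 hits, so at most 11 misses.

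**Where success becomes impossible.** 129 − 65 = 64 hits are needed from the first 75. With 63 or fewer (12 or more misses, observed P30 at most 63/75 = 84.0%), a perfect Cohort 3 gives at most 63 + 65 = 128, which fails. This step needs no assumption about the true P30.

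**How often.** P(12 or more misses in 75), and 65 times that probability as the expected number of evaluable subjects enrolled with no chance of primary success:

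| True P30 | Probability | Expected subjects |
|---|---|---|
| 0.95 | 0.03% | 0.02 |
| 0.92 | 1.6% | 1.0 |
| 0.90 | 6.9% | 4.5 |
| 0.88 | 18% | 12 |
| 0.85 | 45% | 29 |

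**Just short of impossible.** With exactly 11 misses at the interim, success needs 65 of 65. At a true P30 of 0.95 the chance is 0.95^65 = 3.6%.

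**Effect of a stop at impossibility.** Summing exactly over interim counts, the two-stage type I error at 0.85 is 0.0084 (interim) + 0.0061 (final) = 0.0145. Power at 0.95 is 0.6789 + 0.2768 = 0.956. Paths with 12 or more interim misses contribute nothing to either sum, so stopping them changes neither. Expected evaluable subjects in Cohorts 2 and 3 fall from 139.5 to 110.0 at a true P30 of 0.85, from 132.3 to 127.8 at 0.90, and from 95.87 to 95.85 at 0.95.

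**Sensitivity.**
- Success criterion: if the unadjusted 95% CI wording governs (one-sided 0.025), P(X ≥ 128 of 140) = 0.0170 passes. Twelve misses are then allowed and impossibility starts at 13, with probability 33% at a true P30 of 0.85.
- Final size: at n = 142 the 0.0150 test needs 130 hits (exact p = 0.0145) and so also allows 12 misses. The limit depends on a final n that the documents do not fix exactly.

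**The case against.** A group-sequential design that stops only for success is legitimate, and nothing in the documents contradicts it. The plan expects a P30 of 0.95, the sensor keeps the light source and detector of its predecessor, and up to 30 run-in and about 20 Validation Cohort 1 subjects tune and confirm the algorithm first. At 0.95 the impossible state has a probability of 0.03%; the large probabilities arise only if the sensor performs well below expectation. All of this stands. It limits the size of the point but supplies no reason to continue once success is out of reach.

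Cohort 3 also has other uses: the safety and effectiveness objective, the eGFR and skin-type subgroups in SAP 4.1, and the by-site analysis in SAP 8.3. That stands too. However, both documents tie Cohort 3 to the missed primary endpoint and do not give these uses as a reason to enrol it.

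A reader might infer that 12 misses in 75 show a device below its goal. They do not: 63/75 has an exact 95% confidence interval of 73.7% to 91.4%, which includes 85%. It shows only that this trial can no longer declare success.

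A reader might also scale the expected numbers up to dosed subjects by using the enrolment figure of 240. That figure is a ceiling that also covers extra run-in subjects at new sites, and neither document gives a non-evaluability rate for Cohort 3. No dosed-subject number is supported.

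**Conclusion.** The gap is real and modest. As written, the plan enrols Validation Cohort 3 even when primary success cannot occur. For 75 and 140 subjects at 0.0150 this means 12 or more interim misses. The probability is negligible at the planning value (0.03%), 6.9% at a true P30 of 0.90 and 45% at 0.85.

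A reader might infer a flaw in error control. There is none on this point: type I error is 0.0145 against 0.025, and power is 0.956. The matter is avoidable exposure, with a remedy that costs neither alpha nor power.

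That an impossible region exists does not depend on which success wording governs. Its exact start does: the limit of 11 misses rests on a final n of exactly 140, on the 0.0150 criterion, and on interim hits and misses that cannot later change. The last condition is not secured. The primary set excludes PK outliers, and SAP 5.4.3 describes a trend correction and a threshold derived from earlier data without saying clearly whether they are fixed or re-estimated.

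**What to change.** 1. State one governing success criterion, either the exact 0.0150 test or the 95% CI wording, and use it throughout both documents.
2. State a fixed maximum number of evaluable subjects for the final analysis.
3. Fix the PK outlier thresholds before the interim, so that interim misses cannot be reclassified.
4. Add to SAP 8.2 and 8.9 and Protocol 5.1, 5.4.1 and 9.5: *If the misses at the interim already exceed the number allowed at the final analysis at that maximum size under the governing criterion (more than 11 for 140 subjects at 0.0150; more than 12 if the unadjusted 95% CI governs), Validation Cohort 3 is not enrolled and the study ends without primary success.*

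The drafting cost is a few sentences. With items 1 to 3 in place, type I error and power do not change. The loss is the descriptive, subgroup and safety data that Cohort 3 would have provided. If the sponsor wants those data regardless, the plan should give that as a stated reason for enrolling the cohort.
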